### **11.3.2. Abnormal Test Findings**

The criteria for determining whether an abnormal objective test finding should be reported as an AE are as follows:

- Test result is associated with accompanying symptoms, and/or
- Test result requires additional diagnostic testing or medical/surgical intervention, and/or
- Test result leads to a change in trial dosing (*outside of protocol-stipulated dose adjustments*) or discontinuation from the trial, significant additional concomitant drug treatment, or other therapy, and/or
- Test result is considered to be an AE by the investigator or sponsor.

Merely repeating an abnormal test, in the absence of any of the above conditions, does not constitute an AE. Any abnormal test result that is determined to be an error does not require reporting as an AE.

### **11.3.3. Definition of a Serious Adverse Event**

A SAE or serious adverse drug reaction is any untoward medical occurrence at any dose that:

- Results in death;
- Is life-threatening (immediate risk of death);
- Requires inpatient hospitalization or prolongation of existing hospitalization for medical reasons (e.g. prolongation of hospitalization for social reasons is excluded);
- Results in persistent or significant disability/incapacity;
- Results in congenital anomaly/birth defect.

Progression of the cGVHD (including signs and symptoms of progression) should not be reported as a SAE unless the outcome is fatal during the trial or within the safety reporting period. Hospitalization due to signs and symptoms of disease progression should not be reported as SAE.

Medical and scientific judgment should be exercised in determining whether an event is an important medical event. An important medical event may not be immediately life-threatening and/or result in death or hospitalization. However, if it is determined that the event may jeopardize the subject and/or may require intervention to prevent one of the other outcomes listed in the definition above, the important medical event should be reported as serious.

#### **11.3.4. Hospitalization**

AEs reported from clinical trials associated with hospitalization or prolongation of hospitalization are considered serious. Any initial admission (even if less than 24 hours) to a healthcare facility meets these criteria. Admission also includes transfer within the hospital to an acute/intensive care unit.

Hospitalization does not include the following:

- Rehabilitation facilities;
- Hospice facilities;
- Respite care (e.g., caregiver relief);
- Skilled nursing facilities;
- Nursing homes;
- Routine emergency room admissions;
- Same day surgeries (as outpatient/same day/ambulatory procedures).

Hospitalization or prolongation of hospitalization in the absence of a precipitating, clinical AE is not in itself a SAE. Examples include:

- Admission for treatment of a preexisting condition not associated with the development of a new AE or with a worsening of the preexisting condition (eg, for work-up of persistent pre-treatment lab abnormality);
- Social admission (e.g., subject has no place to sleep);
- Administrative admission (eg, for yearly physical exam);
- Protocol-specified admission during a clinical trial (e.g., for a procedure required by the trial protocol);
- Pre-planned treatments or surgical procedures should be noted in the baseline documentation for the entire protocol and/or for the individual subject.

Diagnostic and therapeutic non-invasive and invasive procedures, such as surgery, should not be reported as AEs. However, the medical condition for which the procedure was performed should be reported if it meets the definition of an AE. For example, an acute appendicitis that begins during the AE reporting period should be reported as the AE, and the resulting appendectomy should be recorded as treatment of the AE.

#### **11.4. Severity Assessment**

Treatment related toxicities and other AE and SAE are classified according to the NCI common toxicity criteria (CTC), **specification for stem cell transplantation**, as outlined in the appendix of this protocol. The updated CTC can be downloaded from the worldwide web using the following URL:

[http://evs.nci.nih.gov/ftp1/CTCAE/CTCAE\\_4.03\\_2010-06-14\\_QuickReference\\_5x7.pdf](http://evs.nci.nih.gov/ftp1/CTCAE/CTCAE_4.03_2010-06-14_QuickReference_5x7.pdf)

Please note the distinction between the severity and the seriousness of an AE. A severe event is not necessarily a serious event. For example, a headache may be severe (interferes significantly with subject's usual function) but would not be classified as serious unless it met one of the criteria for SAEs, listed above.

## **11.5. Causality Assessment**

The investigator's assessment of causality must be provided for all AEs (serious and non-serious). An investigator's causality assessment is the determination of whether there exists a reasonable possibility that the investigational medicinal product caused or contributed to an AE.

Not Related: Where a temporal (timely) relationship of the onset of the event, relative to the administration of the investigational medicinal product is not reasonable (e.g. as crash as passenger), or where another cause can explain the occurrence of the event by itself. *[Considered as having not a reasonable possibility to be related to the investigational medicinal product]*

Unlikely: Where a temporal (timely) relationship of the onset of the event, relative to the administration of the investigational medicinal product is unlikely and or because another cause may be suspected. *[Considered as having not a reasonable possibility to be related to the investigational medicinal product]*

Possibly Related: Where a temporal (timely) relationship of the onset of the event, relative to the administration of the investigational medicinal product is reasonable, but the event could have been due to an equally likely cause. *[Considered as having a reasonable possibility to be related to the investigational medicinal product]*

Probably Related: Where a temporal (timely) relationship of the onset of the event, relative to the administration of the investigational medicinal product is reasonable and the event is more likely to be explained by the investigational medicinal product than by another cause. *[Considered as having a reasonable possibility to be related to the investigational medicinal product]*

**Definitely Related:** Where a temporal (timely) relationship of the onset of the event, relative to the administration of the investigational medicinal product is reasonable and there is no other cause to explain the event or a re-challenge is positive. [*Considered as having a reasonable possibility to be related to the investigational medicinal product*]

If the investigator's final determination of causality is unknown and the investigator does not know whether or not investigational medicinal product caused the event, then the event will be handled as "related to investigational medicinal product" for reporting purposes. If the investigator's causality assessment is "unknown but not related to investigational medicinal product", this should be clearly documented on trial records.

In addition, if the investigator determines a SAE is associated with trial procedures, the investigator must record this causal relationship in the source documents and eCRF, as appropriate, and report such an assessment in accordance with the SAE reporting requirements, if applicable.

## **11.6. Exposure In Utero**

For investigational medicinal products within clinical trials and for marketed products, an exposure in-utero (EIU) occurs if:

- 1) a female becomes, or is found to be, pregnant either while receiving or having been directly exposed to (e.g., environmental exposure) the investigational medicinal product, or the female becomes, or is found to be, pregnant after discontinuing and/or being directly exposed to the investigational medicinal product (maternal exposure);
- 2) a male has been exposed, either due to treatment or environmental, to the investigational medicinal product prior to or around the time of conception and/or is exposed during the partner pregnancy (paternal exposure).

If any trial subject or trial subject's partner becomes or is found to be pregnant during the trial subject's treatment with the investigational medicinal product, the investigator must submit this information to Sponsor on an Exposure in Utero Form. In addition, the investigator must submit information regarding environmental exposure to a Sponsor product in a pregnant woman using the Exposure in Utero Form. This must be done irrespective of whether an AE has occurred and within 24 hours of awareness of the pregnancy. The information submitted should include the anticipated date of delivery.

Follow-up is conducted to obtain pregnancy outcome information on all Exposure in Utero reports with an unknown outcome. The investigator will follow the pregnancy until completion or until pregnancy termination (ie, induced abortion) and then notify Sponsor of the outcome. The investigator will provide this information as a follow up to the initial Exposure in Utero Form.

If the outcome of the pregnancy meets the criteria for immediate classification as a SAE (i.e., spontaneous abortion, stillbirth, neonatal death, or congenital anomaly [including that in an aborted fetus, stillbirth or neonatal death]), the investigator should follow the procedures for reporting SAEs.

Additional information about pregnancy outcomes that are classified as SAEs follows:  
“Spontaneous abortion” includes miscarriage and missed abortion.

All neonatal deaths that occur within 1 month of birth should be reported, without regard to causality, as SAEs. In addition, any infant death after 1 month that the investigator assesses as possibly related to the in utero exposure to the investigational medicinal product should be reported.

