### **3. Study design**

This is a prospective, national, multicenter, non-randomized Phase II study that will include a total number of 24 patients.

The duration of participation planned is as follows:

- Duration of recruitment: 34 months
- Study duration for a considered patient: 12 months
- Total duration of the study: 46 months

Several visits are scheduled in the study as follows:

- At the time of diagnosis for the screening visit
- Follow-up visits to be performed every week during ATO treatment
- Follow-up visits to be performed every 2 weeks from second to third month of ATO treatment
- Follow-up visits to be performed every month from the fourth to sixth month of ATO treatment
- Follow-up visits to be performed every 3 months: at 9 months and 12 months (final visit)

Arsenic trioxide is administrated either via the marketed product named TRISENOX® or the investigational medicinal product named ARSCIMED® (Cf. section 5 for more detail).

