## 4. Patients selection

### 4.1 Inclusion criteria

Patient will be eligible for inclusion in this study if the patient met all the following criteria:

- Adult patients ( $\geq 18$  years) who have received a first allogeneic stem cell transplantation for a hematological disease (any source of hematopoietic stem cells is authorized; any category of conditioning regimen prior to allo-SCT is authorized; any type of stem cell donors is authorized)
- Confirmed diagnosis of first episode of chronic GvHD requiring systemic immunosuppressive therapy (any prior GvHD prophylaxis previously used is accepted). Chronic GvHD diagnosis is defined according to the National Institutes of Health (NIH) Working Group Consensus. Chronic GvHD diagnosis will be based on the evaluation of the severity of the different clinical manifestations including:
  - a/ Performance status evaluation
  - b/ Cutaneous evaluation measured by the percentage of extension or the presence of sclerotic features. If relevant, confirmation with a biopsy should be performed whenever possible
  - c/ Oral symptoms
  - d/ Ocular symptoms
  - e/ Gastro-intestinal symptoms
  - f/ Evaluation of liver involvement (total bilirubin, transaminases and alkaline phosphatases)
  - g/ Pulmonary function evaluation
  - h/ Evaluation of the musculoskeletal manifestations, especially the amplitude of the relevant articulations
  - i/ Genital tract symptoms
- Signed informed consent (see Appendix 14)
- Absence of contra-indications to the use of ATO

- Subjects affiliated with an appropriate social security system
- Men must use a medically acceptable method of contraception throughout the treatment period and for at least 4 months and 10 days following the last treatment administration
- Women who are of childbearing potential must have a negative serum pregnancy test and agree to use a medically acceptable method of contraception throughout the study and for 3 months following the end of the study
- Patient not participating or not having participated in a clinical study in the 30 days prior to his/her inclusion in the study

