### **11.2. Reporting Period**

SAEs require immediate notification to Sponsor beginning from the time that the subject provides informed consent, which is obtained prior to the subject's participation in the clinical trial, i.e., prior to undergoing any trial-related procedure and/or receiving investigational medicinal product, through 30 days after the administration of the last dose.

Any SAE occurring any time after the reporting period must be promptly reported if a causal relationship to investigational medicinal product is suspected.

AEs (serious and non-serious) should be recorded on the electronic CRF from the time the subject has taken at least one dose of trial treatment through last subject visit.

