### **11.7.2. Serious Adverse Event Reporting Requirements**

If a SAE occurs, Sponsor is to be notified within 24 hours of awareness of the event by the investigator. In particular, if the SAE is fatal or life-threatening, notification to Sponsor must be made immediately, irrespective of the extent of available AE information. This timeframe also applies to additional new information (follow-up) on previously forwarded SAE reports as well as to the initial and follow-up reporting of Exposure in Utero cases.

For all serious AEs, the investigator is obligated to pursue and provide information to Sponsor in accordance with the timeframes for reporting specified above. In addition, an investigator may be requested by Sponsor to obtain specific additional follow-up information in an expedited fashion. This information may be more detailed than that captured on the AE case report form. In general, this will include a description of the AE in sufficient detail to allow for a complete medical assessment of the case and independent determination of possible causality. Information on other possible causes of the event, such as concomitant medications and illnesses must be provided. In the case of a subject death, a summary of available autopsy findings must be submitted as soon as possible to Sponsor.

It is the investigators responsibility to maintain an accurate and up to date record of all AEs/occurrences in patients participating in the clinical trial. This record, including details of nature, onset, duration, severity, outcome and any relationship to investigational medicinal product, should be noted in the patient s medical notes. It is the investigators responsibility to review all events occurring at their site and as such the investigator must ensure that the patients are not compromised. Any appropriate action must be taken to protect the patients whilst ensuring validity of the results. It is the investigator responsibility to report correctly and on time to the sponsor SAE and to answer to queries at time.

All SAE Form must be sent to the sponsor by fax or e-mail to:

AnticipSanté

[name]

E-mail: [[contact]](mailto:[contact])

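### Section 11.6 counts pregnancies after ATO as in-utero exposures but requires the Exposure in Utero Form only for pregnancies during treatment

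*Protocol*

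**What the plan says.** Section 11.6 of the protocol first defines exposure in utero. The maternal arm includes a woman who becomes or is found to be "pregnant after discontinuing and/or being directly exposed to the investigational medicinal product (maternal exposure". The paternal arm covers a man exposed before or near conception, or during his partner's pregnancy. Neither arm has a time limit after the last dose.

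The next paragraph sets the duty to report. The investigator must submit the Exposure in Utero Form, within 24 hours of awareness, if a trial subject or a subject's partner "becomes or is found to be pregnant during the trial subject's treatment with the investigational medicinal product". The only other trigger is environmental exposure of a pregnant woman. Outcome follow-up then applies to Exposure in Utero reports and is supplied as a follow-up to the initial Form.

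Section 4.1 requires contraception well past dosing. For men it runs through treatment and "for at least 4 months and 10 days following the last treatment administration". For women it runs "throughout the study and for 3 months following the end of the study". The SAP repeats these criteria in its section 9.2.1 and adds no rule on reporting pregnancies.

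**The concern.** The definition and the duty do not match. A woman who conceives a month after her last infusion, or a man whose partner does, meets the definition of an exposure. Neither meets the trigger for the Form. With no initial Form, the stated follow-up to outcome has nothing to start from.

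Some adverse outcomes of such a pregnancy could still reach the sponsor as serious adverse events. What would be lost is prompt notice of the pregnancy, and any record of pregnancies that end normally. The sponsor could then learn of adverse outcomes without knowing how many exposed pregnancies lay behind them. Section 5.1 says the sponsor is developing its own ATO product in this population, so each exposed pregnancy with a known outcome is scarce information.

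**Working it through.** **Does another section close the gap?**

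- *Section 11.7.2* applies the 24-hour timeframe "as well as to the initial and follow-up reporting of Exposure in Utero cases". That sets a deadline for cases being reported. It does not say which pregnancies must be reported.
- *Section 11.2* requires immediate notice of serious adverse events up to 30 days after the last dose. After that: "Any SAE occurring any time after the reporting period must be promptly reported if a causal relationship to investigational medicinal product is suspected". This reaches a suspected adverse outcome, not the pregnancy itself.
- *Section 11.5* treats events of unknown causality as related for reporting. This widens the late rule somewhat, but still only for events.
- *Section 11.3.1* lists signs or symptoms resulting from exposure in utero as possible adverse events. An uncomplicated pregnancy, or a partner's pregnancy, is neither in the subject.
- *Section 11.6* itself makes neonatal death within one month of birth reportable regardless of causality. That is one outcome only.
- *Table 2 and section 7.2* schedule a single serum pregnancy test, before the first dose. No later test would reveal a case.

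None of these makes a post-treatment pregnancy as such reportable.

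**How much of the contraception window lies outside the trigger?** The plan gives no figure to reproduce. The inputs are:

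- Day 1 is the first infusion. The last infusion of a cycle is on day 24 in the example schedule (sections 5.1 and 7.3.2.1).
- Cycle 2 starts 8 to 11 weeks after the first infusion, on day 57 to 78. Its last infusion is on day 57 + 23 = 80 to 78 + 23 = 101.
- Men: window end = last infusion + 4 × 30.4 + 10 = last infusion + 131.6 days.
- Women: window end = 365 + 91 = day 456. This takes the end of the study as the patient's month 12 (section 8.1).
- Sensitivity case for women: 3 months (91 days) after the last infusion. This is an assumption; the documents do not state such a window.

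Uncovered share = (window end − end of treatment) / window end.

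*Treatment taken to end at the last infusion:*

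| | One cycle (day 24) | Two cycles (day 80) | Two cycles (day 101) |
|---|---|---|---|
| Men | 131.6/155.6 = 84.6% | 131.6/211.6 = 62.2% | 131.6/232.6 = 56.6% |
| Women, study end + 3 months | 432/456 = 94.7% | 376/456 = 82.5% | 355/456 = 77.9% |
| Women, last dose + 3 months | 91/115 = 79.1% | 91/171 = 53.2% | 91/192 = 47.4% |

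*Treatment read as running to month 6 (day 183).* Section 3 uses the phrase "Follow-up visits to be performed every month from the fourth to sixth month of ATO treatment", which allows this looser reading.

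| | One cycle | Two cycles (day 80) | Two cycles (day 101) |
|---|---|---|---|
| Men | 0% (window ends day 155.6) | 28.6/211.6 = 13.5% | 49.6/232.6 = 21.3% |
| Women, study end + 3 months | 273/456 = 59.9% | 59.9% | 59.9% |
| Women, last dose + 3 months | 0% (ends day 115) | 0% (ends day 171) | 9/192 = 4.7% |

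**The case against.** The best defence is to read sections 11.6 and 11.7.2 together. A post-treatment pregnancy is an exposure in utero by definition, section 11.7.2 speaks of initial and follow-up reporting of such cases, and otherwise the post-discontinuation part of the definition does nothing. A careful site might well report on that basis. But the sentence in section 11.7.2 is about timing, and the only sentence that says when a subject or partner pregnancy must be submitted limits it to treatment. A site that followed the explicit trigger would be compliant.

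The calculated size is also open to challenge. Treatment is not defined for this purpose, and the shares run from 0% to 95% depending on the reading. That point stands: the figures show that the gap can be large, not how large it is. With the windows that section 4.1 actually sets, only men given one cycle are fully covered on the loosest reading.

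Three further points stand in part. The safety net for adverse outcomes is fairly wide, given the rule on unknown causality and the neonatal-death rule, so the loss is mainly notice and prospective follow-up. The Form and Appendices 12 to 14 are not in the text available and might carry pregnancy instructions, although these would not change the explicit trigger in section 11.6. And with 24 patients, a negative test at entry and mandatory contraception, there may be no case at all.

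A pregnancy conceived during treatment but discovered later is covered, because the trigger includes becoming pregnant during treatment.

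**Conclusion.** The concern holds. Section 11.6 counts post-treatment pregnancies as exposures but does not require the Form for them, and no other section available makes them reportable as such. Counting treatment to the last infusion and using the section 4.1 windows, 57–85% of the men's window and 78–95% of the women's lies outside the trigger. Reading treatment to month 6 reduces this to 0–21% for men and 60% for women. These are shares of calendar time under the example dosing schedule, with study end at month 12. The documents give no pregnancy rate, so no expected count can be calculated; in a trial of 24 patients it will be small. The matter concerns completeness of safety data. It does not touch any endpoint or analysis, and it is worth correcting because the correction is cheap.

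**What to change.** In section 11.6, replace the limit to the subject's treatment with a stated period. It should run from the first ATO infusion until 4 months and 10 days after the last infusion for partners of male subjects, and until 3 months after the end of the study for female subjects. Keep the 24-hour notice and the follow-up to outcome as they are.

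This ties the trigger to windows the protocol already sets and removes any dependence on what counts as treatment. The definition itself would remain open-ended, so pregnancies conceived after the windows close would still meet it without triggering the Form. That remainder lies beyond the period for which the protocol requires contraception.

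The cost is one clause, handled as a protocol amendment through the ethics committee and authorities (sections 13.1 and 13.3). No visit or test is added. Sites would complete a few more forms and would have to report cases they learn of after the final visit.
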